#### 8.4.2 Secondary PK parameters

The secondary PK variable is  $C_{\min,\tau}$ , which is used to describe minimum concentration during the dosing intervals. Statistical evaluation for secondary PK variable will be done using similar methods as for primary variable, except the statistical model will include also the dosing interval as fixed effect.

The following SAS-code for the analysis will be applied:

```
proc mixed data=pkparam2 alpha=0.10;
  class subject trtpcd interval visit;
  model log_auc = trtpcd interval trtpcd*interval visit /
ddfm=KR outp=Resid solution;
random subject*visit;
lsmeans trtpcd trtpcd*interval / diff cl alpha=0.10
adjust=tukey ADJDFE=ROW;
ods output tests3=testCross lsmeans=lsmeansCross
diffs=diffscross;
by group;
run;
```

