8.4.3 Pharmacokinetic analysis

The primary variable for the evaluation of PK of levodopa is AUC_{0-24} to describe the total levodopa exposure. The secondary PK variable is $C_{min,tau}$, which is used to describe minimum concentration during the dosing intervals. The ratio of the C_{max} in a dosing interval and the observed concentration at the end of the dosing interval, $C_{max}/C_{min,tau}$, which is used to describe levodopa fluctuation during the dosing intervals and other PK variables of levodopa, 3-OMD, carbidopa and ODM-104 will be evaluated as other variables.

PK parameters will be analysed after logarithmic transformation and 90% confidence intervals (CIs) for the geometric means will be calculated.

The conclusions regarding possible differences between different study treatments will be based on both overall evaluation of levodopa concentration-time profiles and formal statistical analyses of PK parameters.

Primary pharmacokinetic evaluation

The primary PK variable will be summarised using descriptive statistics by treatment and analysed using a mixed linear model with 90% CI applicable for the crossover design. The statistical model will include treatment and period as fixed effects and subject as random effect. Sensitivity analysis adjusted for subject weight and age will be performed.

Levodopa fluctuation ratios ($C_{\max}/C_{\min,\tau}$, $C_{\max}/C_{(16\text{ h})}$, PTF_{τ} and PTF_{0-16}), and AUC_{0-24} , C_{\max} and $C_{\min,\tau}$ will be the main PK variables of interest.

The primary conclusions will be based on the PP population.

Secondary pharmacokinetic evaluation

Statistical evaluation for secondary PK variable will be done using similar methods as for primary variable. Statistical model for $C_{\min,\tau}$ will include treatment, period, dosing interval, and treatment by dosing interval interaction as fixed effect and subject by period interaction as random effect.

Other pharmacokinetic evaluations

The other PK variables for the evaluation of PK of levodopa, carbidopa, 3-OMD and ODM-104 are presented in [Table 4](#). All PK variables will be summarised by treatment using descriptive statistics. Selected PK variables will be analysed using similar models and sensitivity analysis to the primary and secondary PK variables. Drug concentrations will be tabulated by time and treatment with descriptive statistics.

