#### 8.4.1 Primary PK parameter

The primary PK variable for the evaluation of PK of levodopa is AUC0-24 to describe the total levodopa exposure. The primary PK variable will be summarised using descriptive statistics by treatment and analysed using a mixed linear model with 90% CI applicable for the crossover design. The statistical model will include treatment and period as fixed effects and subject as a random effect. Sensitivity analysis adjusted for subject weight and age will be performed.

The following SAS-code for the primary comparison will be applied:

```
proc mixed data=pkparam2 plots=all alpha=0.10;
  class subject trtpcd visit;
  model log_auc = trtpcd visit / ddfm=KR outp=Resid solution;
  random subject;
  lsmeans trtpcd / diff cl alpha=0.10;
  ods output tests3=testCross lsmeans=lsmeansCross
  diffs=diffscross;
  by group;
run;
```

The following SAS-code for the sensitivity analysis will be applied:

```
proc mixed data=pkparam2 plots=all alpha=0.10;
  class subject trtpcd visit;
  model log_auc = trtpcd visit weightkg age / ddfm=KR outp=Resid
solution;
random subject;
lsmeans trtpcd / diff cl alpha=0.10 adjust=tukey ADJDFE=ROW;
ods output tests3=testCross2 lsmeans=lsmeansCross2
diffs=diffscross2;
by group;
run;
```

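### SAP 8.4.2 names Cmin,tau as the secondary variable, but its prescribed SAS code has log_auc as the response, so run literally it would not analyse troughs

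*SAP*

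**What the plan says.** SAP 8.4.2 introduces Cmin,tau as the variable "which is used to describe minimum concentration during the dosing intervals. Statistical evaluation for secondary PK variable will be done using similar methods as for" the primary variable, with dosing interval added as a fixed effect. It then states: "The following SAS-code for the analysis will be applied". The code opens with "proc mixed data=pkparam2 alpha=0.10", has the model statement "model log_auc = trtpcd interval trtpcd*interval visit", and uses "random subject*visit".

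The primary code for AUC0-24, in SAP 8.4.1, opens with "proc mixed data=pkparam2 plots=all alpha=0.10" and has "model log_auc = trtpcd visit / ddfm=KR outp=Resid solution". The sensitivity code in 8.4.1 uses the same response and data set.

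Protocol 8.4.3 gives the Cmin,tau model in words: it "will include treatment, period, dosing interval, and treatment by dosing interval interaction as fixed effect and subject by period interaction as random effect". The same section calls for PK parameters to be analysed on the log scale. SAP Table 2 marks levodopa Cmin,tau for statistical analysis, and the SAP's table list reserves Table 14.2.1.8.2 for the result.

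**The concern.** The text and the code of SAP 8.4.2 name different response variables. The code is presented as what will be run, not as an example, and all three SAS blocks in the SAP model log_auc.

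Cmin,tau is the only secondary PK variable and is listed in SAP 8.4.3 among the main PK variables of interest. A more stable levodopa profile is the stated attraction of the MR formulation (protocol 1.1), and an AUC result does not describe the trough. An AUC contrast filed under Table 14.2.1.8.2 would answer a different question from the one in the table title.

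SAP 7.2.11 requires a treatment-by-interval term for every parameter calculated by dosing interval. The 8.4.2 block is the only code with that structure, so it is the likely template for the other per-interval variables too.

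**Working it through.** The plan gives no figure to reproduce; the check compares the code with the text.

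**1. Code against the protocol's Cmin,tau model**

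| Element | Protocol 8.4.3 | SAP 8.4.2 code | Match |
|---|---|---|---|
| Response | log Cmin,tau | log_auc | No |
| Treatment (fixed) | yes | trtpcd | Yes |
| Period (fixed) | yes | visit | Yes |
| Dosing interval (fixed) | yes | interval | Yes |
| Treatment by interval (fixed) | yes | trtpcd*interval | Yes |
| Subject by period (random) | yes | subject*visit | Yes |

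Only the response disagrees. That pattern fits a block adapted from 8.4.1 in which the model terms were updated and the response was not.

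**2. What log_auc could contain**

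The derivation of pkparam2 is not shown, so there are two readings.

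- *AUC0-24.* There is one value per subject and period, repeated over four intervals. The interval and treatment-by-interval terms have nothing to explain, and the residual variance collapses to zero.
- *AUCtau.* There are four values per subject and period, and the model runs normally. The output is exposure within each interval. Protocol Table 4 defines Cmin,tau as the observed concentration at 3.5, 7, 10.5 and 14 h, which is a different quantity.

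Neither reading gives a trough contrast.

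**3. Illustration of the mechanics (effects assumed, not from the documents)**

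One data set was simulated for a four-period Williams design with 12 subjects and four intervals. The assumed true D/A ratios were 1.40 for AUC and 2.00 for the trough. The 8.4.2 model was fitted twice.

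| Response | Estimated D/A ratio | Treatment-by-interval estimates (D vs A) | Residual variance |
|---|---|---|---|
| log trough | 2.03 | -0.09, 0.14, -0.05 | 0.038 |
| log AUC0-24, repeated | 1.41 | 0, 0, 0 | 1.5 × 10⁻¹² |

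The code returns the contrast of whatever response it is given. The gap between 2.03 and 1.41 reflects the assumed inputs and says nothing about this trial.

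**The case against.** The strongest reply is that the intent is never in doubt. The sentence above the code, protocol 8.4.3 and its synopsis, SAP Table 2 and Table 14.2.1.8.2 all name Cmin,tau. The primary and secondary blocks also share output names, and the secondary one needs an interval factor that the primary does not. That suggests a working template with names carried over, although this is inference. A programmer would probably notice. If log_auc held AUC0-24, the zero residuals would show in the residual inspection required by SAP 7.2.8, and means on an AUC scale would sit beside the Cmin,tau summary in ng/mL. Conclusions also draw on the overall concentration-time profiles, and Cmin,tau is summarised descriptively as well.

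Most of this stands, and it limits the weight of the point. It does not remove it: the AUCtau reading would run with no such warning sign, and code written into a SAP is meant to spare the programmer from guessing.

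Two stronger readings are tempting and are not supported.

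- *That the plan leaves the Cmin,tau analysis specified nowhere else.* Protocol 8.4.3 and the synopsis give the model in full; 8.4.2 is only the sole code for it.
- *That a trough difference of a particular size would be missed.* Take one-compartment kinetics with four doses 3.5 h apart, absorption rate 3/h for IR against 0.6/h with a 0.5 h lag for MR, and equal bioavailability. A half-life of 2 h gives MR/IR trough ratios of 1.33 to 1.55 with an AUC0-24 ratio of about 0.99. A half-life of 1.5 h gives 1.57 to 1.83, and 3 h gives 1.13 to 1.32. None of these inputs is in the documents. Groups 1 to 3 have no IR arm, and A4 against D4 also differs in carbidopa and ODM-104, so equal bioavailability does not represent any primary comparison. Under the AUCtau reading at 2 h, the ratios would be 0.59, 0.87, 0.96 and 0.99, so even the apparent direction depends on what log_auc contains.

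**Conclusion.** The point holds as a contradiction between the prescribed code and the stated secondary variable. Run literally, SAP 8.4.2 estimates an AUC contrast and not a trough contrast, whichever AUC log_auc holds. This rests on log_auc meaning a log AUC, as it does in 8.4.1; the SAP does not say otherwise.

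It is most likely a copy error, and the intended analysis is clear from the rest of both documents. The size of the discrepancy cannot be derived from the documents, so none is claimed. The primary AUC0-24 analysis and the sample size are unaffected. A reader should not infer that the trial would misreport troughs, only that the code as written needs correcting before it is run.

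**What to change.** In SAP 8.4.2, replace log_auc with the natural log of Cmin,tau, for example a variable named log_cmintau, and state that the input data set has one record per subject, period and dosing interval. Say explicitly that Cmin,tau is log-transformed, because SAP 7.2.9 names only AUC and Cmax as a minimum.

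Add one sentence stating that the same block is run with the matching log response for the other levodopa per-interval variables marked for statistical analysis in SAP Table 2: Cmax,tau, Cmin,tau,actual, AUCtau, Cmax/Cmin,tau, Cmax/Cmin,tau,actual and PTFtau.

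The cost is one variable name, these short clarifications and a check of the program behind Table 14.2.1.8.2. No design, data-collection or sample-size change follows.

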
Statistical methods:
 
PK parameters will be analysed after logarithmic transformation and 90% confidence intervals (CIs) for the geometric means. The conclusions regarding possible differences between different study treatments will be based on both overall evaluation of levodopa concentration-time profiles and formal statistical analyses of PK parameters.
 
Primary pharmacokinetic evaluation
 
The primary PK variable will be summarised using descriptive statistics by treatment and analysed using a mixed linear model with 90% CI applicable for the crossover design. The statistical model will include treatment and period as fixed effects and subject as random effect. Sensitivity analysis adjusted for subject weight and age will be performed. The primary conclusions will be based on the per-protocol (PP) population.
 
Secondary pharmacokinetic evaluation
 
Statistical evaluation of the secondary PK variable will be done using similar methods to the primary variable. Statistical model for $C_{min,tau}$ will include treatment, period, dosing interval and treatment by dosing interval interaction as fixed effects and subject by period interaction as random effect.
 
Other pharmacokinetic evaluations
 
PK variables for the evaluation of PK of levodopa, carbidopa, 3-OMD and ODM-104 will be summarised by treatment using descriptive statistics. Selected PK variables will be analysed using similar models and sensitivity analysis to the primary and secondary PK variables. Drug concentrations will be tabulated by time and treatment with descriptive statistics.

Safety evaluation

AEs and serious adverse events (SAEs) will be summarised by treatment using subject and event counts. Clinical safety variables and their changes from baseline will be evaluated using descriptive statistics. 12-lead ECG abnormalities will be tabulated and the intra-subject differences between visits will be evaluated. Laboratory safety variables will be evaluated using descriptive statistics for the actual values and their changes from baseline. Physical examination and C-SSRS findings will be tabulated.

ABBREVIATIONS AND DEFINITION OF TERMS

3-ODM	3-O-methyldopa
AADC	Aromatic l-amino acid decarboxylase
AE	Adverse event
AUC	Area under the concentration-time curve
BMI	Body mass index
BP	Blood pressure
CA	Competent authority
CI	Confidence interval
C _{max}	Maximum concentration in plasma
C _{min}	Minimum concentration in plasma

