### 7.2.2 Handling of dropouts or missing data

In general, missing data or partial data will not be imputed, and statistical analyses will be performed for observed cases only. Possible missing data will be included in statistical calculations via mixed models theory, where missing data can be utilized by setting the subject as random effect in the statistical model. Possible sensitivity analyses may be carried out to evaluate the robustness of the statistical results, that is, particularly the impact of potential outliers.

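### The Cmin,tau model has no subject effect, so between-subject variance inflates the standard errors, 90% CIs and p-values of the treatment differences

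*SAP*

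**What the plan says.** SAP 8.4.2 gives the code for Cmin,tau. The model line is "model log_auc = trtpcd interval trtpcd*interval visit", the only random statement is "random subject*visit", and the output requested is "lsmeans trtpcd trtpcd*interval / diff cl alpha=0.10", with a Tukey adjustment. Subject appears in neither the fixed nor the random part, except inside the interaction with visit (period).

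The protocol specifies the same random structure. Section 8.4.3 lists "treatment by dosing interval interaction as fixed effect and subject by period interaction as random effect", and the synopsis lists "dosing interval and treatment by dosing interval interaction as fixed effects and subject by period interaction as random effect".

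Elsewhere the plan describes a subject effect:

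- SAP 8.4.1, primary model for AUC0-24: "The statistical model will include treatment and period as fixed effects and subject as a random effect".
- SAP 8.4.2, introducing the Cmin,tau model: "similar methods as for primary variable, except the statistical model will include also the dosing interval as fixed effect".
- SAP 7.2.2, general statement on missing data: "where missing data can be utilized by setting the subject as random effect in the statistical model".

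Protocol 1.2.1 gives the reason for the crossover: it is meant to limit the influence of variability between individuals on the levodopa parameters.

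**The concern.** A random term for subject-by-period alone links the four Cmin,tau values within one period of one subject. It does not link that subject's four periods, so each subject-period is handled as if it came from a different person. Whatever makes one man's troughs consistently higher than another's has nowhere to go except the subject-by-period variance. In each group every subject receives each treatment in a different period, so every treatment comparison is a comparison across periods and carries that inflated variance.

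The treatment differences thus get standard errors appropriate to a parallel-group trial. Cmin,tau is the plan's named secondary variable, and the results are meant to guide the choice of combination for later studies. A real trough difference between combinations could be reported as inconclusive only because the model ignored the pairing.

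**Working it through.** **Inputs.** From the documents: 4 treatments, 4 periods and 4 dosing intervals per group; 12 subjects (3 per sequence) in the power statement and 14 randomised; two-sided 10% level; Tukey adjustment for secondary comparisons (SAP 7.2.6); within-subject SD 0.139 on the log scale, which is for AUC0-24 (Protocol 8.2). The documents give no standard error, power or variance for Cmin,tau, so there is no plan figure for it to reproduce. The 80% power in Protocol 8.2 is for AUC0-24 and is not used here.

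Assumed: between-subject SD sb from 0.1 to 0.4, and a second within-subject SD of 0.25.

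**Formulas.** Let ssp be the subject-by-period SD, se the residual SD and n the subjects per group. The within-subject SD of a period mean is sw = sqrt(ssp² + se²/4). For a treatment difference averaged over intervals:

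- with subject and subject-by-period: variance = 2·sw²/n
- as specified: variance = 2·(sb² + sw²)/n
- SE ratio = sqrt(1 + sb²/sw²)

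At a single interval, sw² is replaced by ssp² + se².

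**SE ratios, averaged over intervals**

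| sb | sw 0.139 | sw 0.25 |
|---|---|---|
| 0.1 | 1.23 | 1.08 |
| 0.2 | 1.75 | 1.28 |
| 0.3 | 2.38 | 1.56 |
| 0.4 | 3.05 | 1.89 |

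Single-interval ratios also depend on how sw divides into ssp and se. With ssp 0.12 and se 0.14 (sw = sqrt(0.0144 + 0.0049) = 0.139), they run from 1.14 to 2.39 over the same sb range. With ssp 0.20 and se 0.30 (sw = sqrt(0.04 + 0.0225) = 0.25), they run from 1.04 to 1.49.

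**Check on the full interval-level model.** Exact generalised-least-squares SEs, using the Group 1 example sequences in Protocol Table 2, n = 12, sb 0.3, ssp 0.12, se 0.14:

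| Quantity | As specified | With subject added |
|---|---|---|
| D minus A, averaged | 0.135 | 0.057 |
| D minus A, one interval | 0.144 | 0.075 |
| LS-mean of D | 0.095 | 0.095 |
| Interval 2 minus 1 within D | 0.057 | 0.057 |

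The first row by hand: sqrt(2 × (0.09 + 0.0193)/12) = 0.135, against sqrt(2 × 0.0193/12) = 0.057. The problem is confined to between-treatment differences.

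**Power for one pair, averaged over intervals, Tukey-adjusted.** Simulation on period means, 40,000 trials per setting. For n = 12 the residual df are 41 as specified and 30 with subject, with critical |t| 2.366 and 2.394. For n = 14 the df are 49 and 36, with critical |t| 2.353 and 2.376.

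| sw | True difference | n | As specified, sb 0.1 / 0.2 / 0.3 / 0.4 | With subject |
|---|---|---|---|---|
| 0.139 | 20% | 12 | 61 / 22 / 4 / 1% | 79% |
| 0.139 | 20% | 14 | 70 / 28 / 6 / 1% | 86% |
| 0.139 | 40% | 12 | 99.7 / 92 / 57 / 22% | >99.9% |
| 0.139 | 40% | 14 | >99.9 / 97 / 70 / 31% | >99.9% |
| 0.25 | 20% | 12 | 24 / 12 / 5 / 1% | 29% |
| 0.25 | 20% | 14 | 28 / 15 / 6 / 2% | 34% |
| 0.25 | 40% | 12 | 76 / 59 / 35 / 17% | 81% |
| 0.25 | 40% | 14 | 84 / 69 / 45 / 23% | 87% |

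**Direction.** Under no difference, with sb 0.3 and n = 12, an unadjusted 10% test rejects 0.1% of the time (sw 0.139) or 1.4% (sw 0.25) as specified, and 10% with subject in the model.

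**The case against.** The specification is consistent: the protocol synopsis, Protocol 8.4.3 and the SAP code all give subject-by-period as the random effect, so this is a prespecified choice and not a slip in one document. That is true, but it only means that both documents need correcting. It does not make the standard errors right.

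The size cannot be derived from the documents. The 0.139 belongs to another parameter, and the remaining variances are assumed. This stands: the tables show how the loss behaves and do not estimate it. At sw 0.25 and a 20% difference, even the corrected model reaches only 29 to 34%, so the omission is not the main problem in that case. The power figures also cover only the average over intervals. The Tukey adjustment over all 16 treatment-by-interval cells needs a critical |t| of about 3.2 to 3.4, and no power is given for those comparisons.

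The harm is bounded. The bias is conservative, Cmin,tau is secondary, no sample-size claim rests on it, and conclusions also draw on the concentration-time profiles. All of this stands and limits the severity. The conservatism was shown for complete data. Removing intervals after emesis from the per-protocol analysis (SAP 7.1) can unbalance the data, and point estimates may then differ between the two models as well.

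Two of the internal conflicts are weak. The sentence in SAP 8.4.2 about similarity to the primary model is loose and also omits the treatment-by-interval interaction that its own code contains. SAP 7.2.2 is a general statement. The conflict with the crossover rationale in Protocol 1.2.1 does not depend on either.

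**Conclusion.** The concern holds. As specified, the model gives standard errors, 90% CIs and p-values for between-treatment differences in Cmin,tau that are too large whenever between-subject variance is above zero, both averaged over intervals and at each interval. This conclusion follows from the model structure and needs no outside figure.

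The size does need assumptions. The loss is small when sb is well below sw (SE ratio 1.08 at sb 0.1, sw 0.25) and severe when sb exceeds sw (3.05 at sb 0.4, sw 0.139).

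Not affected: SEs of single-treatment LS-means, interval comparisons within a treatment, point estimates in balanced data, and the primary AUC0-24 analysis. Other per-interval parameters are affected only if they are analysed with this same model, which Protocol 8.4.3 leaves open. This should be fixed, but it does not threaten the primary conclusion.

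**What to change.** In SAP 8.4.2, change the random statement to `random subject subject*visit;`. In the same code, replace the response `log_auc` with log Cmin,tau. The intended variable is clear from the section text, so this is a minor correction. Use the same random structure for any other per-interval parameter analysed with this model.

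Align Protocol 8.4.3 and the synopsis, or enter the change with its date and reason in SAP 8.7, which has a heading but no content. The SAP table templates carry a May 2017 date and the planned start was February 2017, so data may already have existed. A dated SAP entry is then the practical route, and if results had been seen, the model now in the plan should be reported alongside.

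The cost is one model term and one variable name, with no new data, visits or subjects. If the subject variance is estimated as zero, the corrected model reduces to the present one.

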6.2.3 Calculation of pharmacokinetic variables

Table 4 lists the PK parameters which will be derived from the concentration-time data of levodopa, carbidopa, 3-OMD and ODM-104.

Table 4. PK parameters to be calculated for levodopa, carbidopa, 3-OMD and ODM-104

Parameter	Levodopa	Carbidopa	3-OMD	ODM-104
C_{max}	X ¹	X ¹	X ¹	X ¹
$C_{max,tau}$	X ¹			X
t_{max}	X	X	X	X
$t_{max,tau}$	X			X
$C_{min,tau}$	X ¹			X
$C_{min,tau,actual}$	X ¹			
AUC_{tau}	X ¹			X
AUC_{0-16}	X ¹			
AUC_{0-24}	X ¹	X ¹	X ¹	X ¹
AUC_{∞}	X			X
$t_{1/2}$	X			X
λ_z	X			X
$C_{max}/C_{min,tau}$	X ¹			
$C_{max}/C_{min,tau,actual}$	X ¹			
$C_{max}/C_{(16h)}$	X ¹			
PTF_{tau}	X ¹			
PTF_{0-16h}	X ¹			

¹ Statistical analysis will be performed

C_{max}	The maximum observed concentration of the concentration-time curve
$C_{max,tau}$	The maximum observed concentration for each dosing interval
t_{max}	The time to reach the maximum observed concentration
$t_{max,tau}$	The time to reach the maximum observed concentration for each dosing interval
$C_{min,tau}$	The observed concentration at the end of each dosing interval i.e. concentration at 3.5 h, 7 h, 10.5 h and 14 h
$C_{min,tau,actual}$	The observed minimum plasma concentration after each dose before the concentration starts to rise due to the following dose. For the 4th dosing interval, the plasma concentration at time 16 h will be used as the minimum plasma concentration.
AUC_{tau}	The area under the concentration-time curve calculated with linear trapezoidal rule for each dosing interval
AUC_{0-16}	The area under the concentration-time curve calculated with linear trapezoidal rule from time 0 to the 16 h PK sample
AUC_{0-24}	The area under the concentration-time curve calculated with linear trapezoidal rule from time 0 to the 24 h PK sample
AUC_{∞}	The area under the concentration-time curve from time 0 to infinity, AUC_{∞} will be determined by adding area under the concentration-time curve from time 0 to the last sample with a quantifiable concentration (AUC_t) to the extrapolated area that will be

	determined by dividing the last quantifiable concentration by λ_z
$t_{1/2}$	The terminal elimination half-life that is calculated with the equation $\ln 2 / \lambda_z$
λ_z	The terminal elimination rate constant from the log-linear portion of the concentration-time curve after the last (10.5 h) dose

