## 6 Determination of sample size

The sample size estimation is based on earlier ODM-104 phase I study 3112003. Sample size is estimated using the  $AUC_{0-24}$ . Sample size estimation is based on the results from 12 subjects that completed treatment periods with levodopa 100 mg / carbidopa 25 mg / entacapone 200 mg and MR levodopa 100 mg / carbidopa 65 mg / ODM-104 100 mg. The latter treatment arm with ODM-104 and 65 mg of carbidopa increased exposure by 22% ( $AUC_{0-24}$  14022.2 vs. 17092.6). Within subject variability is estimated to be 0.1386 ( $\sqrt{MSE}$  in logarithmic scale). It is assumed that MR levodopa 100 mg / carbidopa 65 mg / ODM-104 100 mg will increase exposure by 40% compared to MR levodopa 100 mg / carbidopa 25 mg.

When the sample size in each sequence is 3 (with a total sample size of 12), a crossover design will have 80% power to detect a difference in means of 0.336 assuming that the within subject variation is 0.139 using a crossover ANOVA with a 0.1 two-sided significance level. To allow drop outs 14 subjects per group and 56 subjects in total will be randomized into this study with 4-treatment, 4-period William's crossover design. This will provide adequate power for the primary comparison. In case there are premature discontinuations the sponsor will decide case-by-case whether replacement subjects will be entered into the study. Replacement subjects will be randomized to go through all 4 treatment periods. Discontinued study subjects are not allowed to re-enter the study.

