## 7.2 Statistical issues

### 7.2.1 Significance level and confidence intervals

90% confidence intervals and p-values will be produced between different treatments. A two-sided significance level of 10% will be considered the level of statistical significance. Confidence intervals and p-values will be presented up to four decimal places.

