#### **7.2.6 Multiplicity**

For the primary comparisons, there is only one primary comparison in each group, thus multiplicity correction is not needed. For secondary comparisons, where several treatments are included, all pairwise comparisons will be adjusted according to Tukey method.

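### The interval-level Tukey family for Cmin,tau in SAP 8.4.2 spans all 16 treatment-by-interval cells, so same-interval treatment limits are 11–13% wider than joint 10% error control requires

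*SAP*

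**What the plan says.** SAP 7.2.6 gives the multiplicity rule: "For secondary comparisons, where several treatments are included, all pairwise comparisons will be adjusted according to Tukey method". SAP 7.2.1 says that confidence intervals and p-values are for differences between treatments, and sets the level: "A two-sided significance level of 10% will be considered the level of statistical significance". SAP 7.2.11 asks only that the treatment-by-interval interaction be in the model for parameters derived per dosing interval. None of these sections says which pairs form the family at interval level.

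The code in SAP 8.4.2 fits "model log_auc = trtpcd interval trtpcd*interval visit" with "random subject*visit", by group. It then asks for "lsmeans trtpcd trtpcd*interval / diff cl alpha=0.10", continued by "adjust=tukey ADJDFE=ROW". Nothing in the code limits the interaction differences to pairs from the same interval.

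SAP 6 describes a "4-treatment, 4-period" crossover in each group. Protocol 6.2.3 defines Cmin,tau at the end of four dosing intervals, "i.e. concentration at 3.5 h, 7 h, 10.5 h and 14 h".

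**The concern.** The text describes adjusting comparisons between treatments, but at interval level the code adjusts over every pair of cells. That includes, for example, treatment A in the first interval against treatment D in the fourth, which no section of either document asks for. Each added pair raises the critical value for the pairs that matter.

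Cmin,tau is the only named secondary PK variable, and SAP 8.4.3 lists it among the main variables of interest. The development rationale (Protocol 1.1) is a more stable levodopa profile over the day, and the results are to guide the choice of combination (Protocol 2.1). Trough differences at each dosing interval bear directly on that choice, so unnecessary width in their limits has a cost even though it cannot inflate false positives. Any other by-interval variable analysed with the same code (AUCtau, Cmax,tau, Cmin,tau,actual, the per-interval fluctuation ratios) would carry the same excess.

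**Working it through.** The plan states no multiplier or interval width for Cmin,tau, so there is no figure to reproduce. The check takes the response in the 8.4.2 code to be log Cmin,tau.

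**Inputs.** Four treatments and four periods per group (SAP 6); four dosing intervals (Protocol 6.2.3); two-sided alpha 0.10 (SAP 7.2.1); 14 subjects per group (SAP 6).

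**Pairs.** Cells: 4 × 4 = 16. All pairs: 16 × 15 / 2 = 120.
- Different treatments, same interval: 4 intervals × 6 treatment pairs = 24.
- Same treatment, different intervals: 4 treatments × 6 interval pairs = 24.
- Different treatments, different intervals: 120 − 24 − 24 = 72.

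**Degrees of freedom.** With 14 complete subjects there are 56 subject-periods and 224 observations.
- Subject-period stratum: 56 − 7 = 49.
- Within-period stratum: (224 − 56) − 12 = 156.
- Total: 205.

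The range 49 to 205 covers the plausible values for a same-interval treatment difference.

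**Formula.** A Tukey half-width is q(0.90; k, df)/√2 × SE, where k is the number of means in the family. The SE of a given difference does not depend on the family, so the ratio of multipliers is the ratio of widths on the log scale. Bonferroni over m pairs uses t(1 − 0.10/(2m); df). Tukey within interval plus Bonferroni over four intervals uses q(0.975; 4, df)/√2.

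| Family | df 49 | df 150 | df 205 |
|---|---|---|---|
| As coded: Tukey, 16 cells | 3.330 | 3.240 | 3.228 |
| Bonferroni, 24 same-interval pairs | 3.006 | 2.910 | 2.898 |
| Tukey within interval, Bonferroni over 4 | 2.939 | 2.856 | 2.846 |
| Tukey, 4 treatments, per interval only | 2.353 | 2.311 | 2.306 |

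**Excess width of the coded limits.**
- Over Bonferroni on 24 pairs: 1.108, 1.113, 1.114, so about 11%.
- Over within-interval Tukey with Bonferroni: 1.133, 1.134, 1.134, so about 13%.
- Over per-interval Tukey: 1.415, 1.402, 1.400, so about 40%.

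The first two alternatives hold the error at or below 10% over all 24 same-interval treatment pairs jointly. The third holds it at 10% within each interval only. Over four intervals that would be 1 − 0.9⁴ = 34% if the intervals were independent, and at most 40%.

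**Sharper joint method.** Both joint alternatives are bounds. A simulation of the exact joint critical value for the 24 pairs (large df, assumed correlation between intervals in the same period of 0 to 0.95) gives 2.80 down to 2.49, against a coded multiplier of 3.196 at near-infinite df. The excess is then 14% to 28%, so 11–13% does not overstate the gap.

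**The case against.** The strongest case against is that the family is a matter of judgement, and the code does what 7.2.6 literally says: it adjusts all pairwise comparisons by Tukey. That stands. A reader might infer that text and code contradict each other. They do not; the text leaves the interval-level family undefined.

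A reader might also take the 40% as pure waste, equivalent to about half the subjects since (2.311/3.240)² = 0.51. That is not supported either. Most of the 40% comes from moving from joint control over four intervals to control within each one. It is the price of a stricter guarantee, not lost information.

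Nor are all 96 cross-interval pairs irrelevant. The 24 that compare a treatment with itself across intervals bear on how levels drift through the day, a theme of Protocol 1.1. If those 24 and the 24 same-interval pairs are taken as one family, Bonferroni over 48 pairs gives 3.133 at 150 df, and the coded limits are only about 3% wider (3.240/3.133 = 1.034). But the documents do not ask for those comparisons, and SAP 7.2.1 speaks of treatments.

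Two limits on scope also stand. The same statement requests the treatment main effect, which PROC MIXED adjusts separately over four means. The output also contains unadjusted 90% limits, and no template shows which set will be reported for Cmin,tau, although 7.2.6 points to the adjusted set.

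Harm is not quantified. The documents give no variance or expected difference for Cmin,tau, and conclusions also rest on overall evaluation of the concentration profiles (SAP 5).

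**Conclusion.** The point holds with limited size. As coded, the adjusted 90% limits for same-interval treatment differences in Cmin,tau are about 11–13% wider on the log scale than methods that keep joint 10% control over the 24 pairs of interest. The figure is about 40% only if the sponsor accepts a separate four-treatment family per interval. Both figures are stable over 49 to 205 df.

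They rest on two assumptions: that same-interval treatment contrasts are the comparisons of interest, which fits SAP 7.2.1 and 7.2.6 but is not stated, and that the adjusted limits are the ones reported.

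The effect is conservative. It does not touch the overall Cmin,tau treatment differences, the unadjusted limits or the primary AUC0-24 analysis. A reader might infer that real trough differences will be missed; the documents support only that the adjusted limits are less precise than they could be.

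**What to change.** Split the LSMEANS request in SAP 8.4.2. Keep the treatment main effect as it is, with Tukey and row-specific degrees of freedom. For the interval level, replace the interaction term by a comparison of the four treatments within each interval, for example `slice trtpcd*interval / sliceby=interval diff cl adjust=tukey`. Use alpha 0.025 per interval (0.10/4, Bonferroni over four intervals) if joint control is kept, or 0.10 if control per interval is accepted. Retain row-specific degrees of freedom where the statement allows it, and add the slice differences to the ODS output, because the existing request will not capture them.

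In SAP 7.2.6, state the interval-level family, whether error is controlled jointly over intervals, and which limits are reported. Apply the same rule to the other by-interval variables.

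The cost is a line or two of code and a few sentences of text, with no new data. The downside is that same-treatment comparisons between intervals leave the adjusted family; if they are wanted, they should be reported as a separate, declared family. Without the Bonferroni step, error is controlled per interval only, and the SAP should say so.
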